10. **Electrocardiogram (ECG/EKG):** Heart rate can change during various levels of arousal as measured by a 12-lead ECG system (Mortara Instruments). ECG may be measured during the anxiety task or CO₂ administration.

11. **Electric Field Modeling:** Electric field simulation will include segmenting the structural MRI scan from a single subject into white matter, cortical matter, cerebrospinal fluid, skull, scalp, eyes, fat, muscle and air using Simpleware ScanIP. The volumes defining head tissues and the attached electrodes will be meshed into finite elements using the Simpleware module. The electric field will be computed using COMSOL simulation software. The electric field will be calculated in the LC and other brain regions thought to be relevant to our tDCS effort including prefrontal cortex, limbic system structures, and brain stem, which will be segmented using Brain Parser, and manually checked per published guidelines. For multielectrode targeting optimization we will first construct a head model with a multi-electrode grid. We solve for the component field solutions by sequentially activating individual electrodes relative to a reference. We then define a desired field distribution, which takes relatively large values near the target (LC), and zero value everywhere else in the brain.

8.11 INSTRUMENTS: List all questionnaires, surveys, interview, or focus group guides that will be used for this study:

1. **Mini-International Neuropsychiatric Interview (MINI).** The MINI is a short structured diagnostic interview for DSM-IV and ICD-10 psychiatric disorders. It will be used to screen potential subjects for neuropsychiatric disorders and has acceptable reliability and reliability when used for this purpose.
2. **Treatment Tolerability Ratings.** In order to determine the tolerability of particular tDCS electrode placement and electrical stimulus intensities, subjects will rate their discomfort immediately after each tDCS stimulus on a 5-point Likert scale that has been widely used to assess the tolerability of procedures including colonoscopy, nasogastric tube insertion, burn dressing application, and orthodontic procedures. The anchors are: 0="No Discomfort", 1="Minimal Discomfort", 2="Mild Discomfort", 3="Moderate Discomfort", and 4="Severe Discomfort". We employ a cutoff of no more 2 as an indicator of acceptable tolerability.
3. **Visual Analogue Scale for Anxiety (VAS-A).** The VAS-A is the primary measure of clinical symptoms of Acute Fear in both the R21 and R33. It has been used extensively as an indicator of acute fear symptoms. It is included because it provides a reliable indicator of rapid changes of affective state and is sensitive to the fear-inducing effects of 7.5% CO₂ in healthy volunteers. VASA consists of 11 items for 11 different symptoms (anxious, alert, fearful, relaxed, happy, feel like leaving, paralyzed, tense, nervous, irritable and worried) where for each item a mark is made on a 100 mm line scaled from 0 (not at all) to 100 (the most ever) to indicate symptom severity. The "Fearful" item will be used as the single primary endpoint due to its being consistently significantly increased in prior studies of CO₂ administration to healthy controls and evidence that anxiolytics can prevent 7.5% CO₂ mediated increases in this measure. The other 10 VAS-A items will be secondary outcomes. For each CO₂ administration ratings will be carried out at baseline (5 min prior to inhalation), and at 5, 10, 15, and 20 minutes into the inhalation and 15 minutes after inhalation ends. The peak effect will be obtained immediately after the end of the inhalation when the subjects will be asked to retrospectively rate the greatest intensity of effects experienced. A 26% increase in peak effect over baseline on the "fearful" item will be utilized as criteria for responding to CO₂ challenge as recommended based on prior work which suggests that approximately 50% of subjects will meet this criterion. The VAS-A "fearful" rating at 20 minutes from the start of CO₂ administration will serve as the primary outcome measure with the rating of peak effect being a key secondary outcome. The VAS-A may also be used during the anxiety task before, during, or after to measure changes in levels of subject anxiety from baseline to post-task administration.
4. **State Trait Anxiety Inventory (STAI).** The 20 item STAI will be included as a secondary clinical symptoms measure of state anxiety occurring with CO₂ administration. This was included because it has well-established psychometric properties and reflects changes in anxiety level with CO₂ administration in healthy controls and anxiolytic medication attenuated the CO₂ response with this measure. It consists of 20 items listing feelings and subjects rate their

current state with respect to those feelings from 1 (not at all) to 4 (very much so). It will be administered just before and just after CO₂ administration.

5. **Generalized Anxiety Disorder-7 (GAD-7)**. The 7 item questionnaire may be administered at screening visits to identify anxiety state and trait correlations with pupil physiology.
6. **Beck Anxiety Inventory (BAI)**. This questionnaire may be administered at screening visits to identify anxiety state and trait correlations with pupil physiology.
7. **Adverse Effects (AE) Assessment**. The Systematic Assessment for Treatment Emergent Events (SAFTEE) will be used to monitor AEs. It is reliable and valid and used by [name] in prior studies.

Attach any unpublished instruments in the 'Other Study Documents' section of the Initial Review Submission Packet form after completing the study application. Published instruments should NOT be attached.

8.12 * BIOSPECIMEN COLLECTION: Are you drawing any blood or collecting other biosamples (e.g. tissue, buccal swabs, urine, saliva, hair, etc.): (REQUIRED)

Yes No

8.25 STATISTICAL METHODS: Briefly summarize the methods and types of analyses that will be performed:

All dependent measures will be tested for distribution normality and meeting homogeneity of variance requirements for parametric statistics. Data transformations will be conducted where indicated.

1. Primary Hypotheses.

R21. Testing R21 hypotheses equates to testing if the "Go-No-Go" criteria for proceeding to the R33 are met.

1) Hypothesis 2a: We can identify an electrode configuration for active tDCS that is well-tolerated (5-point Likert scale rating mild discomfort) and significantly suppress the Anxiety Task or Auditory Oddball

Task (AOT) pupil dilation response in 8/10 subjects in the 3rd round of treatment optimization. The Anxiety Task or AOT response will be determined using a repeated measures analysis of variance * (RMANOVA) with condition (common vs rare) as the independent measure and pupil diameter as the dependent repeated measure. If there is a statistically significant difference between the two conditions during treatment it will be assumed that suppression did not occur.

2) Hypothesis 1b: In 10 controls in a cross-over study, 7.5% CO₂ inhalation significantly increases the VAS-A "fearful" rating compared to baseline rating. This will be tested with a RMANOVA where condition (7.5% CO₂ vs air) is the independent variable and VAS-A "fearful" rating is the repeated dependent measure.

3) Hypothesis 2a, 1b, 1a: In a cross-over study, active dose-personalized tDCS significantly suppresses the LC pupil response to 7.5% CO₂. This will be tested by carrying out a RMANOVA where treatment (active tDCS vs control) is the independent variable and mean resting pupil diameter is the repeated dependent measure. This will also establish that 7.5% CO₂ elicits an LC response as measured by mean pupil diameter (Hypothesis 1b) and whether subjects can guess whether they received active tDCS or the control to assess the viability of the control treatment (Hypothesis 1a).

4) Hypothesis 2b: Active tDCS will be safe in terms of there being no adverse effects of more than mild severity and rated to be possibly, probably, or definitely related to treatment.

R33 Testing R33 hypotheses assesses if the criteria for proceeding to further development are met.

1) Hypothesis 3a: Dose-personalized tDCS decreases VAS-A "fearful" rating compared to sham in a parallel-group, randomized, double-blind study. This will be determined by computing the effect size in terms of Cohen's D for the tDCS vs control treatment effect on the VAS-A "fearful" rating at the expected peak CO₂ effect (20 minutes after start of CO₂).

2) Hypothesis 3b: tDCS is safe as indicated by the absence of adverse effects of more than mild severity rated to be possibly, probably, or definitely related to treatment.

Secondary/Exploratory Analyses. Examples of Exploratory/Secondary analyses of interest include: 1) Testing if there are significant differences between active tDCS and the control therapy on the pupillary response to CO₂ in the R33 study; 2) Evaluating tDCS vs control treatment effect sizes for

other VAS-A items and the STAI in the R33 study; 3) mapping the time-course of effects on LC post-tDCS

8.26 REFERENCES: List only the 5-10 most relevant references (a separate bibliography can be attached for reference purposes if this study involves novel approaches, agents, or an emerging technology that the IRB may not be familiar with):

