8.4 DESIGN: Briefly describe the study design (e.g., observational, interventional, randomized, placebocontrolled, blinded, cross-over, cross-sectional, longitudinal, pharmacokinetic, etc.):

Design & Procedures

1. Subject recruitment: Participants will be recruited in [name] laboratory at UCSF. We plan to enroll a total of 240 subjects healthy volunteers (age range: 21-65 years) in order to complete 100 for the entire effort (R21 and R33 Phases combined). This corresponds to enrolling 68 subjects in the R21 (34/year) and 172 (58/year) during the R33 phase. This takes into account the expected rate of failure to: have a pupillary response to the fear conditioning paradigm (25%) and CO₂ challenge (50% - relevant for last 10 R21 and all R33 subjects); and to meet other screening criteria (see inclusion and exclusion criteria sections). These subjects will be recruited from the local community using posted flyers.

2. R21/R33 Components: R21 Phase:

First 30 Subjects, following the screening visit, these subjects will undergo 2-3 sessions separated by 1 week in which a promising electrode configuration (three promising configurations will each be tested in a cohort of 10 subjects) will be used with tDCS stimulation at increasing electrical dosage during which pupillometry will be carried out to determine the Anxiety Task (a test of responses to electrical pulses delivered to the fingers) or Auditory Oddball Test (AOT; a test of responses to rare vs common sounds) response. During pupillometry while undergoing tDCS, ECG, EEG, respiratory rate, or galvanic skin conductance measures may be obtained. A maximum of 5 total tDCS dosages and sham will be tested.

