Last 10 Subjects. These subjects will take part in a double-blind, controlled, randomized, cross-over study over 3 sessions following their screening visit. At session 1 subjects will undergo electrical dose titration with the tDCS electrode configuration resulting from the 3 rounds of optimization using the same procedure as in the first 30 subjects to determine the lowest well-tolerated dose that suppresses the pupil dilation response to the Anxiety Task or Auditory Oddball Test, except that a maximum of 5 tDCS dosages will be tested at this session. At the second and third sessions (1 week apart) subjects will receive doseoptimized tDCS and the control treatment with order randomized along with 7.5% CO₂ (to evoke an LC response) for 20 minutes. The 7.5% CO₂ will be delivered pre-mixed as provided by Airgas. 7.5% CO₂ is commonly and safely used in the field of study. A mixture of CO₂ 7.5%/O₂ 21%/N 71.5% will be purchased premixed from Airgas and shipped to UCSF. At these sessions, the VAS-A and STA-I will be administered 5 minutes prior to and just after the 20 minute session and VAS-A will also be obtained at 5, 10, 15, and 20 minute points of the CO₂ inhalation. tDCS will be administered during the last 5 minutes of the 20 minute CO₂ inhalation period. Subjects will be monitored for an hour post-session for safety and will undergo study physician assessment to determine suitability to leave. Following the 2nd treatment session participation will end except that subjects will be called the next day to assess for adverse effects and appropriate care will be given if any are found.

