R33 Phase: 60 subjects will participate in a double-blind, randomized, controlled, parallel-group trial. They will be randomized to either active or control treatment and at the first post-screening visit they will undergo electrical dose titration as described above for the treatment they are randomized to. For all titrations, during the 5 minutes between tDCS treatments an unblinded member of the study team not having contact with the subjects will compute their Anxiety Task or Auditory Oddball Test response (these tests will be used to determine optimal dosing in terms of the tDCS level that blocks the pupil response in these tests) and convey to the tDCS treatment physician whether to continue or stop titration. Subjects randomized to the control treatment will undergo a sham titration where the stop level will be randomly selected from the distribution of titration outcomes occurring in the R21 phase. Subjects will then return in 1 week and undergo optimal dose tDCS or control treatment for a single treatment session as described in the prior paragraph. Primary outcome will be the VAS-A "fearful" rating obtained at the end of tDCS/CO₂ inhalation. Anxiety Task or AOT pupil responses will be obtained every 10 minutes after the end of the tDCS/CO₂ inhalation period to map the duration of persistent effects on LC (heart rate and skin conductivity will also be obtained as exploratory measures). At the end of this session participation will end except that subjects will be called the next day to assess for adverse effects and care given if necessary. Data from the R21 phase will be used to provide justification for the larger R33 study, and prior to initiation of the R33 phase, the study will be submitted to the IRB for review/approval.

8.5 BACKGROUND AND SIGNIFICANCE: Briefly provide the background and significance of this study (e.g.

why is this study needed) (space limit: one half page):

If this is a first in humans study, please summarize the safety data from the animal studies. For pediatric drug or device studies, please identify if this is the first study in pediatric populations.

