Because of the novel nature of the proposed work and that the adverse effects profile of the form of tDCS we propose to study is not well-documented, we have set up a Data and Safety Monitoring Board (DSMB) for both the R21 and R33 phases of the proposed effort. The individuals who serve on the DSMB were chosen in conjunction with NIH Program staff and have extensive experience conducting clinical trials and are highly familiar with the proposed methodology. The DSMB will convene every 6 months to review ongoing study procedures, discuss AEs and other safety issues, and to evaluate ongoing methods for maintaining data integrity and confidentiality. They will be provided with a summary of all AEs, outcome data, progress data and subject ratings of treatment tolerability prior to each meeting. They will play a critical role in working with the PI and NIH Program to assess whether the "Go-No-Go" criteria are met for proceeding to the R33 phase. If a decision is made to proceed, they will then monitor the R33 study. Should the DSMB members develop any concerns on the basis of information provided to them by the PI, they may request to examine hard or electronic copies of the participants' research records or other information. In transferring information to the DSMB participants' identities will be protected by transferring only data that are de-identified (hard copies) and/or encrypted (electronic data). In considering the frequency of meetings, we have tried to strike a proper balance between maintaining participant safety and the integrity of the study, and the consequent time and workload. Traditionally, DSMBs convene once a year. However, given the novel nature of this trial and that the risks of the form of tDCS we are administering are not well documented it was felt that every 6 month meetings were appropriate. After each meeting the DSMB will compile the information gained from the monitoring activities and subsequently prepare a report summarizing findings. Also included in the report is their recommendation to continue or discontinue the study. This report is completed and delivered to the NIH and the PI. If the DSMB concludes that the study should be terminated, this opinion will be conveyed to the UCSF business officials as well in the case of this latter type of recommendation. Subsequently the PIs, appropriate business officials at UCSF, and NIH Program will likely discuss the matter further before a final decision regarding study termination is made.

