
Local Monitoring of Subjects, Rules for Withdrawing Participants from Study Interventions, and Safety Stopping Rule: All subjects who undergo tDCS treatments will be carefully monitored locally by one of the study physicians. A study physician will be in the room with all subjects when any study procedures are carried out. There will be close monitoring of the tolerability of each of the tDCS electrode configurations studied. In order to determine the tolerability of particular tDCS electrode placement and electrical stimulus intensities, subjects will rate their discomfort immediately after each tDCS stimulus on a 5-point Likert scale that has been widely used to assess the tolerability of procedures including colonoscopy, nasogastric tube insertion, burn dressing application, and orthodontic procedures. The anchors are: 0="No Discomfort", 1="Minimal Discomfort", 2="Mild Discomfort", 3="Moderate Discomfort", and 4="Severe Discomfort". We employ a cutoff of no more 2 as an indicator of acceptable tolerability. We will employ the following stopping rule for each tDCS configuration test: "If any tDCS electrode configuration is rated at 3 or higher by 3 subjects, all testing with that electrode configuration will cease." In addition, if there is an SAE consisting of the development of new neuropsychiatric symptoms, the study will be halted until the cause of the symptoms is ruled not to be due to the study and, if such an event is determined to be related to the study, the study will not be restarted until modifications to the study methods are made that reduce the risk of such an event recurring based on a review and approval by the DSMB. Any subject who rates tolerability as 3 or greater for any electrode configuration will be withdrawn from further participation. Subjects will be informed that, at any time, they may request to the study physician that study procedures stop and this will occur. This includes that they will specifically be told that they should indicate if they would like tDCS stimulation to

stop during stimulation and it will cease and that they should indicate if they would like to stop CO2 inhalation during the CO2 inhalation procedure and that procedure will immediately be terminated.

Plan for Conducting and Reporting Interim Analysis and Stopping Rule

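### The next-day adverse-effect call is stated only after the final session of the last 10 R21 subjects and the R33 treatment session, so late-starting events in the first 30 R21 subjects and in early exits may go uncounted in a zero-event safety criterion

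*Combined protocol and SAP*

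**What the plan says.** Two places in section 8.4 (Design) provide a next-day call. For the last 10 R21 subjects, who take part in a "cross-over study over 3 sessions following their screening visit", it comes after the final session: "Following the 2nd treatment session participation will end except that subjects will be called the next day to assess for adverse effects". For R33 it comes after the single treatment session: "At the end of this session participation will end except that subjects will be called the next day to assess for adverse effects".

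For the first 30 R21 subjects, section 8.4 says only that "these subjects will undergo 2-3 sessions separated by 1 week". Neither section 8.9 item 3 (Anxiety Task visits) nor section 11.13 (time commitment) adds a contact after the last visit.

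Section 13.2 (Local Monitoring) ends participation for poor tolerability: "Any subject who rates tolerability as 3 or greater for any electrode configuration will be withdrawn from further participation". Section 8.9 item 2 also ends it at titration, either for discomfort above mild or when maximum amperage is reached without effect. Neither section states any later contact.

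In section 8.25 the R21 safety criterion is Hypothesis 2b: "Active tDCS will be safe in terms of there being no adverse effects of more than mild severity", counting effects rated possibly, probably or definitely related. Hypothesis 3b is the R33 counterpart. Neither states how long after stimulation events are counted.

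**The concern.** Hypothesis 2b is one of the Go-No-Go criteria for moving to R33, and a single related event above mild severity fails it. A criterion of that kind depends on how completely events are sought. Here one verdict covers subjects observed in two ways: 10 are called the day after their last exposure, and 30 have no stated contact once they leave. Those 30 are the first to receive the candidate electrode configurations, at rising dosage.

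Subjects who leave before the final session, some of them because stimulation was uncomfortable, do not reach the session that triggers the call. If a headache, skin reaction or other symptom starts or worsens after a last or only session, nothing in the text would lead to its being recorded unless the subject reports it. Any such loss can only make the result look safer. The plan itself says that "the adverse effects profile of the form of tDCS we propose to study is not well-documented", and it already uses a next-day call elsewhere.

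**Working it through.** **Inputs** (section 8.4): first 30 subjects, 2-3 sessions each; last 10, 3 sessions each (one titration, two treatment); R33, 60 subjects with one titration visit and one treatment session. Every session is counted as a stimulation session, active or control.

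**The plan's own figure.** 30 + 10 + 60 = 100, which matches the stated target of 100 completers.

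**What follows each session, for completers**

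| Group | Sessions | Next-day call | Later scheduled visit | Neither |
|---|---|---|---|---|
| First 30 | 30 × 2 to 30 × 3 = 60-90 | 0 | 30 × 1 to 30 × 2 = 30-60 | 30 |
| Last 10 | 10 × 3 = 30 | 10 | 10 × 2 = 20 | 0 |
| R21 total | 90-120 | 10 | 50-80 | 30 |
| R33 | 60 × 2 = 120 | 60 | 60 × 1 = 60 | 0 |
| Both phases | 210-240 | 70 | 110-140 | 30 |

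- R21 completers with no stated contact after their last session: 30/40 = 75%.
- R21 sessions followed by neither a call nor a visit: 30/120 = 25% to 30/90 = 33%.
- Both phases: 30/240 = 12.5% to 30/210 = 14.3%.
- R33 completers without a call: 0 of 60.

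The documents do not forecast early exits, so these cannot be counted. Nor is it stated whether a subject withdrawn from one of the first three cohorts counts among its 10. Either way, no contact is stated after that subject's last session.

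**What the call could add (illustration only).** Suppose no delayed event is seen among n subjects called. The exact one-sided 95% upper bound on the delayed-event risk is 1 − 0.05^(1/n):

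- n = 10: 25.9%
- n = 40: 7.2%

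The chance of seeing at least one delayed event at true risk p is 1 − (1 − p)^n. The values of p are assumptions.

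| Assumed p | n = 10 | n = 40 |
|---|---|---|
| 2% | 18% | 55% |
| 5% | 40% | 87% |
| 10% | 65% | 98% |

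Both calculations treat the 40 as having a common risk. That is a simplification, because the last 10 also inhale CO2.

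**The case against.** The plan does much more than make the call. Under section 12.3 every tDCS subject is assessed with the SAFTEE after each stimulation and asked about named side effects. The duration of any symptom is monitored, and a medical practitioner assesses the subject if it has not cleared within an hour. Section 13.2 puts a study physician in the room for all procedures. Both stated calls follow sessions that include a CO2 challenge, which the first 30 do not undergo, so the difference may be deliberate.

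This stands, and it rules out several stronger readings that a reader might infer:

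- **That these subjects leave without follow-up or are not offered care.** Section 12.3 contradicts this for any event that begins before departure.
- **That everyone withdrawn for discomfort goes uncalled.** A subject who rates 3 or more at a final treatment session has reached the session that triggers the call. The gap concerns exits before that session, and there the text is silent; it does not exclude a call.
- **That calls follow only 8-11% of R21 sessions** (10/120 to 10/90), leaving the rest uncovered. The quotient is right, but 50-80 of those sessions are followed by a further visit where an event can be picked up.
- **That withdrawal hides poor tolerability.** The discomfort rating is recorded before withdrawal and feeds the configuration stopping rule and the interim analyses in section 13.2.

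The objection does not reach events that begin or worsen after the last visit. Questioning before departure cannot find those, and no later visit follows. The stated one-hour observation of every subject applies to CO2 sessions only. The different exposure may explain a difference in follow-up, but the plan does not give that reason, and Hypothesis 2b makes no distinction between the groups.

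**Conclusion.** The point holds in a limited form. Ascertainment of adverse events after the last exposure is uneven within R21: stated for 10 completers, not stated for 30, and not stated in any phase for those who exit before the final session. Related events that start or worsen after departure may therefore be missed in these subjects, and the zero-event Go-No-Go criterion has no stated window that would settle whether they count.

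A reader might go further and conclude that both safety verdicts miss delayed events. The documents do not support that. Every R33 completer is called, so for Hypothesis 3b the gap is confined to early exits. In R21 the last 10 are called, and events after non-final sessions can surface at the next weekly visit.

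The direction of any error is towards a favourable safety result. Its size is unknown, because no delayed-event rate is given. The finding assumes 2-3 sessions for each of the first 30 and that no contact is arranged elsewhere. The consent form was not available for this check and might mention one; even so, the design section should state it.

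**What to change.** In section 8.4, for all three groups, and in section 13.2, state that the existing next-day call is made after the last tDCS exposure of every subject, including those who leave at titration or are withdrawn for discomfort. In section 8.25, state one common adverse-event observation window for Hypotheses 2b and 3b. The two hypotheses as written exclude nobody, so the set of subjects counted need not change.

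With the call extended, stated contact after the last session rises from 10 to 40 of 40 R21 completers and from 70 to 100 of 100 overall, plus early exits. The cost is about 30 short calls by existing staff, one more for each early exit, and a line in the consent form. No dose, schedule or withdrawal rule changes. The downside is that the safety figures may look slightly less favourable.
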